## Research Plan

### BACKGROUND AND SIGNIFICANCE

**BACKGROUND.** Traumatic brain injury (TBI) is a direct cause of long-term cognitive disability in returning Veterans. TBI is also an established risk factor for psychological health and community re-integration. Studies emphasize the dramatic impact of neurological injuries among OEF/OIF/OND active duty troops (see

**Figure 1**). There is mounting evidence to suggest that executive dysfunction due to central nervous system (CNS) insult causes both short-term and long-term consequences resulting in poor goal-directed behavior and significant decrease in independent functioning in both soldiers and returning Veterans. Given the necessity for operational effectiveness in the battlefield environment, executive function symptoms become significant for the military because they jeopardize active duty troops' executive function for crucial decision making. At the same time, while remaining undetected, neurological problems cause poor self-management skills resulting in maladjustment and low quality of life in returning military Veterans. In this study we will use the Individuals with Disabilities Education Improvement

Act of 2004 definition of the traumatic brain injury that describes it as "...an acquired injury to the brain caused by an external physical force, resulting in total or partial functional disability or psychosocial impairment, or both, that adversely affects a person's professional and educational performance in one or more areas, such as cognition; language; memory; attention; reasoning; abstract thinking; judgment; problem-solving; sensory, perceptual, and motor abilities; physical functions; information processing; and speech. The term does not

apply to brain injuries that are congenital or degenerative, or to brain injuries induced by birth trauma. The exposure to stressors from combat including explosive blasts and loss or injury to self or comrades can lead to significant problems when translating back to civilian life post-combat. Due to advances in medicine and body armor, soldiers are surviving blasts or explosions that may have previously resulted in severe injury or death during combat. Following the US defense causality report in November 2009, the Institute of Medicine updated its statistics to show that “casualty-to-wounded ratios have been found for OEF as 1:5.52 and for OIF as 1:7. compared with 1:2.6 in Vietnam and 1:1.7 in World War II.”

Many Veterans returning from the wars in Iraq and Afghanistan Operation Enduring Freedom (OEF), Operation Iraqi Freedom (OIF), and Operation New Dawn (OND) may have experienced TBI, the significance of which is underscored by a national study, undertaken by the RAND corporation commissioned by the Office of the Secretary of Defense for Health Affairs, to gage the impact of TBI on the lives of Veterans and their families. Even if there are no other co-existing physical impairments, TBI and PTSD are enough to significantly hinder a Veteran’s successful progression into active community participation and employment. Physical factors affecting community re-integration in Veterans with polytrauma and traumatic brain injury include pain, PTSD-related anger, and depression. Among psychosocial factors that affect community functioning in returning Veterans are social isolation, poor problem-solving of everyday difficulties, and lack of motivation to change.

[figure not shown]
## EXECUTIVE FUNCTIONING SYSTEM IN TBI: A MULTIFACTORIAL MODEL

Executive dysfunction is the core condition underlying neurologic impairments resulting from central nervous system (CNS) insult such as traumatic brain injury dual TBI-spinal cord injury and stroke, as well as a distinct feature of CNS degenerative disorders such as Parkinson’s disease. As a central clinical syndrome, executive functioning is defined as a network of processes that are responsible for initiating, guiding, and regulating psychomotor, cognitive, emotional, and behavioral functions, particularly, during active and novel problem-solving.

## EXECUTIVE SYSTEM: NEUROANATOMICAL - NEUROCOGNITIVE DIMENSION

Executive processes are thought of as part of the system that acts in a supervisory capacity in the overall brain hierarchy and provide for purposeful, goal-directed behavior. There is a plethora of neurologic and behavioral data demonstrating that individual performance processes are deeply involved with changes in what can be named the executive functional system (EFS) (see *Figure 2 below*). Recent studies emphasize that executive processes do not have a single neuroanatomical representation in the central nervous system, rather they present as patterns merging different brain structures (e.g., the brain’s prefrontal zone and limbic system) and their peripheral counterparts (e.g., motor apparatus). Existing interlinkages in the brain-peripheral system are currently explored by measuring various aspects of executive functioning through standardized neuropsychological assessments, magnetic-resonance imaging (MRI) and a more precise assessment, diffusion tensor imaging (DTI). The conceptual definition of the EFS proposes two major subsystems: the *central executive subsystem*, that includes higher level processes such as selective attention, working memory, and decision-making capacity and the *peripheral executive subsystem*, composed mainly of psychomotor processes associated with central executive performance. Executive functioning can break down at any stage in the behavioral sequence be it volition control, planning, purposeful behavior, or effective performance. Deficiencies in self-initiated behaviors may result from neurological damage to the frontal-subcortical or fronto-limbic circuitry (see *areas C and D, Figure 2*), to the right hemisphere, or in diffuse neurologic conditions (see *area A, Figure 2*). The dorsal prefrontal cortex is critical to allocating attentional resources involved with working memory tasks, or to the attentional controller – a system responsible for maintaining and switching attention.

*Cognitive and psychomotor goal-directed activity*

**Figure 2. Central-Peripheral Dysregulation in Executive Functional System (EFS)**

Patients with subcortical involvement display executive dysfunction that includes impairments in cognitive flexibility, memory recall, and psychomotor slowing. Impairment of executive processes often presents the major challenge in individual ability to perform activities of daily living (ADLs), management of disability, and community reintegration.

#### EXECUTIVE SYSTEM: TBI, PTSD AND COMMUNITY RE-INTEGRATION

There is an overlap of symptoms between TBI and PTSD. This issue is most pertinent in the chronic TBI population where there are higher rates of PTSD. Sustaining any kind of physical injury is known to increase a person's risk for PTSD. There are several symptoms that are found in *both* PTSD and TBI, such as deficits in attention and memory, irritability, and sleep disturbance. However in the acute assessment of TBI, some of the distinguishing symptoms such as headache, dizziness, balance problems, and nausea/vomiting may help to elucidate TBI from PTSD. Another distinguishing factor is the history that is obtained from the patients about the course of events before, during, and after the traumatic event. Loss of consciousness (LOC) and post-traumatic amnesia are less common in PTSD and is the distinguishing historical factor to diagnose mild and moderate TBI.

Research has suggested a range of post-injury cognitive, somatic, and behavioral symptoms including headache, anxiety, dizziness, and memory difficulties immediately following TBI, as well as decreased educational attainment and limitations in work performance. The effects of cognitive and behavioral impairment on independence and societal participation following TBI is well established. At the same time the gaps between research and everyday life continue to exist. As the recent report on the needs of returning IOF/OEF Veterans, published by the U.S. Institute of Medicine, indicates, "little research has been conducted to evaluate whether service members who undergo third location decompression (that is, for service members to have time with their comrades and peers in a restful situation and prepare themselves for going back to their families and communities) have better outcomes than those who do not."

Strengthening the community integration of Veterans with TBI requires a collaborative effort bringing together Veterans and their families, Veterans Health Administration case managers and social workers, and the broader research community to address barriers that prevent Veterans with serious injuries such as TBI from

Motor performance is an instrumental component of the executive functional system. In the classic methodology of motor examination tasks developed by Luria and his successors the ability to copy hand movements paced by a metronome was found to be sensitive to frontal damage and to temporal lesions (see area C, Figure 2). Inability to move rapidly through a repetitive or mixed-movement sequence, combined with errors and perseverations, was found to be characteristic of patients with left hemisphere lesions (see area B, Figure 2). Motor regulation deficits are often associated with withholding responses, based on a "go/no-go" rule where a subject should respond only to one of two presented signals (see area A, Figure 2).

effectively pursuing opportunities in life that are available to others. In one of the first national surveys of OIF/OEF combat Veterans enrolled in the Department of Veterans Affairs health care system, Sayer and colleagues (2009) explored the prevalence and types of community re-integration problems faced by Iraq and Afghanistan war Veterans, while assessing preferences for interventions to promote adaptation to civilian life. Stratified Poisson regression was used to determine whether the number of community reintegration problems and the number of services of interest were associated with the presence of probable PTSD, gender, or race. An estimated 25% to 56% of the population had some to extreme difficulty in social functioning, productivity, community involvement, and self-care domains. At least one third reported divorce, dangerous driving, increased substance use, and anger control problems since returning from deployment. An estimated 41% had probable PTSD and each type of reintegration problem was more prevalent among Veterans with probable PTSD. The vast majority (96%) of Iraq/Afghanistan veterans expressed interest in services to help them readjust to civilian life. The most commonly preferred ways to receive reintegration service or information was at a VA facility, through the mail, and over the internet. Interest in self-help techniques and yoga/meditation was particularly common. Penk and colleagues (2010) in their VHA comparative effectiveness study discussed the need for research that identifies ways to aid Veterans with dual diagnoses attain competitive jobs. Community re-integrations tools were found to be key to the effectiveness of employment programs providing Veterans not only with income-earning work but also with skills to help them secure employment.

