### **Hypothesis:**

H0:  $\mu_1 = \mu_2$  where  $\mu_1$ = mean change in CRIS subscale from time 1 to time 2 in self-management group and  $\mu_2$ = mean change in CRIS subscale from time 1 to time 2 in supported discharge group  
H1:  $\mu_1 \neq \mu_2$

**Power Calculation:** PASS (Power Analysis and Sample Size Software, Kaysville, UT, 2008) was used for the power calculation. The primary outcome of this study is the frequency of social interactions measured via the Extent of Participation subscale of the CRIS. The power calculation was performed based on the hypothesis listed above by using a two-sided t-test with assumption of normality. The level of significance was set at 0.05 and power was set at 90%. The effect size and standard deviation used for the power calculation were estimated based on a previous VA study and clinical judgment. 44 subjects in each

[figure not shown]
group, for a total of 88 subjects will provide 90% power to test an effect size of 0.71 with a SD of 7 for difference in CRIS subscale score between groups with  $\alpha=0.05$  (two sided). After adjustment for 20% loss to follow-up, we will recruit 55 subjects in each group of this study, a total of 110 subjects.

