## RANDOMIZATION OF THE COMPASS PARTICIPANTS

Randomization of the study participants will occur after all the baseline data are collected. The mTBI diagnosis including operational definition of executive dysfunction will be determined by the study Co-PI, [name], Director of the TBI Program at the DC VAMC with the participation of the DC VAMC neuropsychologist as part of the routine evaluation of Veterans referred with suspected TBI. Staff performing all outcome assessments will be blinded to group assignment throughout the study, and participants will be asked at each assessment not to reveal their group assignment to data collectors.

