### **Hypothesis 1: Outcome Variables Main Effects for Community Re-integration Factors**

This algorithm is based on the assumption that an interaction between the intervention group and control groups can be modeled as a fixed effect. An LMM will then be used to evaluate whether the intervention had an effect at any time point or whether the intervention influenced change (growth, trajectory) in the outcome over the course of the study. The following will be considered for the analytical strategy:

- ANOVA, Repeated-measures ANOVA as well as MANCOVA will be used to compare the effect of the COMPASSgoal intervention vs. supported discharge group determined via baseline assessment. ANOVA will be used to compare the change from pre- to post-intervention between the two groups. Furthermore, in order to analyze the main effect of the COMPASSgoal intervention over time, a two-way repeated measures parametric ANOVA, as well as a non-parametric repeated measures Friedman ANOVA, will be performed, using the baseline time point, levels of TBI self-efficacy, or real-world tasks performance as the dependent variables. The levels of the repeated measures factor correspond to the number of assessments: baseline (pre-intervention) and 2 months post-intervention. The between-groups factor will be the intervention group vs. the supported discharge group. MANCOVA analysis will focus on the contrast in TBI self-efficacy between the intervention and supported discharge groups while accounting for a specified covariate: level of executive impairment as defined by FrSBE. In the case of non-normal residuals, we will use a nonparametric repeated measures approach. In the case of missing data, an LMM, which uses a maximum likelihood estimate to correct for unequal number of measures per subject, will be employed.
- *We will use Linear mixed models to control for potential confounding variables and baseline values will be utilized as a covariate. These models will allow for the additional control of potential within subjects clusters. These clusters, though not part of the formal hypothesis testing but byproducts of these models, will allow for conceptualization of additional future hypotheses.*

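### The Hypothesis 1 comparison of CRIS Extent of Participation has no fixed covariate set and does not commit to adjusting for baseline PTSD, although PTSD is measured before randomization and the plan links it to reintegration problems

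*Combined protocol and SAP*

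**What the plan says.** **PTSD and the outcome domain.** The section on TBI, PTSD and community re-integration cites a national survey of combat Veterans: "An estimated 41% had probable PTSD and each type of reintegration problem was more prevalent among Veterans with probable PTSD". The Background also names PTSD as an obstacle to community participation.

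**Measurement and timing.** Table 2 includes the PCL, a 20-item PTSD self-report. The randomization section states: "Randomization of the study participants will occur after all the baseline data are collected". Baseline PCL is therefore known before allocation. That section names no stratification factor, and Overall Study Population speaks of balancing only age, gender and education.

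**Sizing.** The primary outcome in the power section is the CRIS Extent of Participation subscale, and mean change from pre- to post-intervention is compared "by using a two-sided t-test with assumption of normality". The stated result is "90% power to test an effect size of 0.71 with a SD of 7 for difference in CRIS subscale score between groups" with 44 per arm, and then "After adjustment for 20% loss to follow-up, we will recruit 55 subjects in each group of this study, a total of 110 subjects".

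**Analysis of Hypothesis 1.** The SAP says "ANOVA will be used to compare the change from pre- to post-intervention between the two groups". The only covariate it names for Hypothesis 1 is the FrSBe, in a MANCOVA on TBI self-efficacy rather than CRIS. A second bullet says the team will "use Linear mixed models to control for potential confounding variables and baseline values will be utilized as a covariate", without listing those variables. The two approaches are not ranked.

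**Other mentions of PTSD.** The SAP Overview lists PTSD severity among possible stratification variables, depending on the hypothesis, and does not tie it to Hypothesis 1. Hypothesis 2 treats PTSD level as part of a mediating psychosocial profile.

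**The concern.** The plan presents PTSD as a correlate of reintegration difficulty and collects it in time to use it as a baseline covariate, yet the CRIS comparison does not commit to using it. Two things are at stake.

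The first is prespecification. With an ANOVA and a mixed model side by side and an open list of confounders, the covariates behind the headline CRIS estimate could be settled after the data are seen.

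The second is efficiency. If baseline PTSD predicts the analysed outcome, leaving it out keeps explainable variation in the error term, and a chance difference in PTSD between arms moves the realized estimate. A covariate believed to be prognostic belongs in the model whether or not the arms turn out to differ on it.

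**Working it through.** **Inputs from the documents.** Two-sided alpha 0.05; power 90%; effect size 0.71; SD 7; 44 evaluable per arm; 20% loss; PTSD prevalence 41% in the cited survey.

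**Assumptions, not in the documents.** Partial correlation r of baseline PTSD with the analysed CRIS outcome of 0.2 to 0.3, with zero also considered; 41% prevalence in the trial sample.

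**1. The plan's own figure.** Reading 0.71 as a standardized difference gives 0.71 × 7 = 4.97 CRIS points. The normal approximation needs 42 per arm for 90% power and the noncentral t needs 43. At 44 per arm the noncentral t gives power 0.909. Inflation: 44 / (1 − 0.20) = 55 per arm, 110 in total. The figure reproduces. Read as a raw difference of 0.71 points with SD 7, it would need 2043 per arm, so the standardized reading is the intended one.

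**2. Standard error without adjustment.** 7 × sqrt(2/44) = 1.49 points.

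**3. Precision gained by adjusting.** The residual SD is 7 × sqrt(1 − r²), so the effective standardized difference is 0.71 / sqrt(1 − r²).

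| r | r² | effective d | SE (points) | power at 44 per arm |
|---|---|---|---|---|
| 0 | 0 | 0.710 | 1.49 | 0.909 |
| 0.2 | 0.04 | 0.725 | 1.46 | 0.919 |
| 0.3 | 0.09 | 0.744 | 1.42 | 0.932 |

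The one or two degrees of freedom spent on covariates change these powers by no more than about 0.0001.

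**4. When the gain is zero.** The survey association concerns the presence of problems, whereas the sized endpoint is change. If PTSD shifts CRIS equally before and after, the shift cancels in the change score. In an illustrative simulation with a level-only PTSD effect (gap 0.5 to 0.8 SD, pre-post correlation 0.5 to 0.7), the R² of PTSD for change was about 0. The extra R² after adjusting for baseline CRIS was 0.01 to 0.06.

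**5. Size of chance imbalance.** The SD of the between-arm difference in PTSD proportion is sqrt(2 × 0.41 × 0.59 / 44) = 0.105, or 10.5 percentage points. The 95% range is ±1.96 × 10.5 = ±20.6 points, and the chance of a difference of 10 points or more is 0.34.

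**6. Effect of imbalance on the unadjusted estimate.** The implied difference in outcome between Veterans with and without PTSD is 7r / sqrt(0.41 × 0.59), which is 2.85 points at r = 0.2 and 4.27 at r = 0.3.

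- One-SD imbalance: 2.85 × 0.105 = 0.30 and 4.27 × 0.105 = 0.45 points. That is 6% to 9% of 4.97, or 0.2 to 0.3 of a standard error.
- Imbalance at the edge of the 95% range (20.6 points): 0.59 to 0.88 points, or about 0.4 to 0.6 of a standard error.

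**The case against.** Four objections have force.

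**The plan does provide for adjustment.** The Hypothesis 1 mixed model includes baseline values and potential confounders, and the Overview mentions stratifying by PTSD. A reader might infer that the CRIS comparison ignores PTSD altogether; the text does not support that. What stands is that PTSD is not named in any Hypothesis 1 model, the list is open, and neither the ANOVA nor the mixed model is designated primary.

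**No imbalance-triggered rule is written.** A reader might take the confounder wording to mean that covariates are added once the arms are seen to differ. The SAP contains no such rule. The wording is merely unspecific.

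**The evidence is weaker than it looks.** The survey gives no size of association, is cross-sectional, and concerns the presence of problems rather than change in one CRIS subscale. PTSD cannot be called a strong predictor of the endpoint on this basis, and lost precision is possible rather than shown. The 41% may not carry over either: the recruitment-assessment sample, said to resemble trial invitees, leaves out documented clinically significant PTSD, and Table 1 excludes severe psychiatric illness. In the other direction, the plan reports higher PTSD rates in chronic TBI, and Table 1 does not name PTSD as an exclusion. Using PCL total as a continuous covariate does not depend on 41%.

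**Chance imbalance is not bias.** The unadjusted test keeps its type I error, and its standard error already includes this variation. Imbalance matters only for the estimate conditional on the allocation that occurred.

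It can also be said that choosing PTSD over other baseline measures, such as the FrSBe or BSI-18, is partly judgement. That is fair. The case for PTSD is that the plan itself cites it in connection with reintegration, and further covariates could be fixed in the same sentence.

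**Conclusion.** The point holds as a minor one. The CRIS comparison lacks a single primary model with a fixed covariate set, and a baseline variable that the plan itself links to the outcome domain is available but not committed to.

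The unadjusted analysis is valid and the planned 110 is adequate with or without adjustment. The precision gain runs from about zero (PTSD affecting level only, change score analysed) to an increase in power from 0.909 to about 0.92 to 0.93 (partial correlation 0.2 to 0.3, assumed). Under that correlation and an assumed 41% prevalence, a typical chance imbalance would shift the estimate by less than a third of its standard error. A reader might infer a biased COMPASS effect or a definite loss of power, but the documents support neither. The surer benefit is closing an open choice of model.

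**What to change.** In the Hypothesis 1 section of the SAP, name one primary analysis of CRIS Extent of Participation, either ANCOVA or the linear mixed model. State that it includes baseline CRIS and baseline PCL total (continuous) as covariates, whatever imbalance is observed. Let this fixed list replace the reference to potential confounders, and label the ANOVA on change as supportive.

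Use only the baseline PCL. Later PCL values are measured after randomization and belong to the Hypothesis 2 mediation analysis, so they should not enter the Hypothesis 1 model.

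The cost is one sentence and one or two degrees of freedom, with no new data and no change in sample size. The wording should be settled before outcome data are compared by arm; the timeline places an interim analysis 13 months into the project.
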